##### All Trials

1. Overall well-being at 6-month follow-up
2. Sub-domains of overall well-being: pain interference, physical function, sleep disturbance, social role and activities functioning, fatigue, anxiety, and depression at 6-month follow-up
3. Concordance between metabolizer phenotype and prescribed medication

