#### All Trials

*PROMIS 43* – Adults ( $\geq 18$  years of age) will complete a 43-question survey assessing well-being and sub domains: pain interference, physical function, sleep disturbance, social role and activities functioning, fatigue, anxiety, and depression.[32] This survey will be administered to adult participants at baseline, 1-month, 3-months, and 6-months post-surgery (acute pain), or baseline, 1-month, 3-months, and 6-months post return of results (chronic pain, depression).

*PROMIS pediatrics 37* – Pediatric study participants (ages 8-17) will complete a 37-question survey assessing pediatric well-being and sub domains: pain interference, physical function, sleep disturbance, social role and activities functioning, fatigue, anxiety, and depression. This survey will be administered to pediatric participants at baseline, 1-month, 3-months, and 6-months post-surgery (acute pain), or baseline, 1 month, 3 months, and 6 months post return of results (depression).

*Health care utilization* – Survey of the number of significant cost driver health care encounters (e.g. hospitalizations, clinic visits, etc.). This survey will be administered to participants at 10-day, 1-month, 3-months, and 6-months post-surgery (acute pain), or baseline, 1-month, 3-months, and 6-months post return of results (chronic pain, depression).

**Medications** - Participant medications will be collected using patient surveys at baseline and the primary endpoint time points: 10-days for Acute Pain and 3-months for Depression and Chronic pain.

**Productivity loss** – Survey of loss of work the time and pay lost due to the participant's depression or pain. This survey will be administered to participants at 1-month, 3-months, and 6-months post-surgery (acute pain), or 1-month, 3-months, and 6-months post return of results (chronic pain, depression).

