#### Depression

To determine the effect of genotype-guided drug therapy on depression symptoms in depression

participants, we will conduct a subset analysis comparing change in depression T-scores from baseline to 3-month follow-up in the Intervention group subset with either CYP2D6 PM or UM or CYP2C19 PM, RM or UM phenotypes to the Control group subset with CYP2D6 PM or UM or CYP2C19 PM, RM, or UM phenotypes. Participants that have other CYP2D6 or CYP2C19 phenotypes will not be included. Pediatric depression T-scores will be transformed to the adult scale using a published crosswalk for a combined analysis. The baseline to 3-month change in depression T-scores of the Intervention CYP2D6 PM/UM or CYP2C19 PM/RM/UM group will be compared to the baseline to 3-month change in depression T-scores of the Control CYP2D6 PM/UM or CYP2C19 PM/RM/UM subgroup using a two-sided two-sample t-test with a type 1 error of 0.049. This primary analysis will be conducted according to a modified intent-to-treat design, with participants analyzed and endpoints attributed according to the treatment arm to which the participants were randomized, regardless of subsequent crossover or post-randomization medical care.

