## 10.5 Analysis of the Secondary Endpoints

### All Trials

To determine the effect of genotype-guided drug therapy on overall well-being and the well-being sub-domains (pain interference, physical function, sleep disturbance, social role and activities functioning, fatigue, anxiety, and depression) in acute pain, chronic pain, and depression participants, we will conduct an intent to treat analysis, comparing the well-being (or sub-domain) T-scores from the 6-month follow-up assessments in the Intervention group compared to the control group using a two-sided two-sample t-test or Mann Whitney test, as appropriate, stratified by participant population (acute pain, chronic pain, depression), with a type 1 error of 0.05.

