### 11.2 Data Element Definitions

Clinically significant pain reduction: Whether or not the pain reduction score is  $\leq 0.7$ . If the pain reduction score is  $\leq 0.7$ , clinically significant pain reduction is achieved, if pain reduction scores is  $> 0.7$ , clinically significant pain reduction is not achieved.

Depression symptom control: The change in the PROMIS Emotional Distress - Depression 8b or PROIMIS pediatric Depression 8a survey depression score from baseline to time t.

Depression remission: A. Whether or not the summed raw PROMIS emotional distress depression 8b survey responses are  $\leq 16$ , which is equivalent to the participant responding “rarely” or “never” to most or all of the PROMIS emotional distress - depression 8b survey questions. B. Whether or not the PHQ-8 scores are  $\leq 4$ , which is equivalent to depression severity being none-mild.

Depression (PHQ-8) score: The sum of the responses to the PHQ-8 survey, range from 0 to 24.

Depression (T) score: The T-score converted summed responses to the PROMIS emotional distress depression 8b survey. The T-score conversion is centered around 50 with standard deviation of 10.

Depression severity: The depression score converted to depression severity (none, mild, moderate, severe) based on the scoring guide for the PROMIS emotional distress depression 8b survey.

Medication adherence: The scored responses to the Voils Medication Adherence survey.

Medication concordance: Whether or not the medication the participant is prescribed after the intervention is concordant with the participants CYP2D6 and, for the depression trial, CYP2C19 phenotype.

Medication side effects severity burden: (Depression only) The sum of the scored severity (none = 0, mild = 1, moderate = 2, severe = 3) for common SSRI side effects.

Opioid misuse score: The T-score converted summed responses to the PROMIS prescription medication misuse 7a survey. The T-score conversion is centered around 50 with standard deviation of 10.

Opioid persistence: Defined as  $\geq 1$  opioid prescription refill between 90 days and 180 days after the surgical procedure.

Opioid usage: The average daily morphine equivalents in mg (MED) in past 7 days. MEDs will be calculated using data from the opioid usage survey.

Overall well-being: Defined as the T-score converted summed responses to the PROMIS 43/PROMIS 37 pediatrics survey. The T-score conversion is centered around 50 with standard deviation of 10.

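### Overall well-being is a single summed score over problem and ability domains with no scoring direction or reversal rule, so functional gains may partly offset symptom gains

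*Combined protocol and SAP*

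**What the plan says.** Section 11.2 (Data Element Definitions) describes overall well-being in these words: "Defined as the T-score converted summed responses to the PROMIS 43/PROMIS 37 pediatrics survey". It adds only that the T-score is centred at 50 with a standard deviation of 10.

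Section 7.3 gives adults the 43-item form and participants aged 8 to 17 the 37-item form. It lists the same domains for both: "pain interference, physical function, sleep disturbance, social role and activities functioning, fatigue, anxiety, and depression".

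Section 3.2 makes overall well-being at 6 months a secondary endpoint in all trials and lists the sub-domains as a further one. Section 10.5 (All Trials) plans an intent-to-treat analysis "comparing the well-being (or sub-domain) T-scores from the 6-month follow-up assessments in the Intervention group" with those of the control group. It uses a two-sample t-test or Mann Whitney test at 0.05, stratified by trial population only.

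The depression primary analysis in Section 10.4 does treat the age forms as needing a link: "Pediatric depression T-scores will be transformed to the adult scale using a published crosswalk for a combined analysis".

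**The concern.** Five of the named domains are problems (pain interference, sleep disturbance, fatigue, anxiety, depression). Two are abilities (physical function, social role and activities). A total over both kinds has a clear meaning only if every item points the same way, and Section 11.2 does not say that it does.

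Where the plan does reveal a direction, a higher score means more of the named concept. Section 7.3 says that higher pain intensity values mean more intense pain. Section 11.2 defines depression remission as a low raw sum, reached by answering rarely or never to most items. Carried over to the ability domains, that convention gives the literal sum mixed signs.

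The effect on overall well-being is a stated objective of all three trials, and the score is compared in all randomised participants. Section 10.9 reads secondary results by consistency across endpoints rather than by adjusted p-values, which requires an endpoint with a known sign. By contrast, Section 11.2 gives the SIA score's components, transformation, range and the meaning of negative and positive values.

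**Working it through.** The plan gives no effect size or power for this endpoint, so there is no figure to reproduce. The calculation below is conditional and illustrative.

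**Inputs from the plan.** Seven domains (Section 7.3), classed by name as five problem and two ability. Two-sided alpha of 0.05 (Section 10.5). Completers per arm of 845 (acute pain), 447 (chronic pain) and 678 (depression) (Table 9).

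**Assumptions not in the plan.** Ability items are scored higher = better and summed unreversed. Domains are standardised and equally weighted. Once aligned, they share a common correlation rho of 0.3, 0.5 or 0.7. Each domain that improves does so by d = 0.2 SD.

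**Step 1, variances.** With all domains aligned, the variance of the sum is 7 + 7×6×rho = 7 + 42rho. With two domains unreversed, the signs sum to 5 − 2 = 3, so the variance is 7 + (3² − 7)rho = 7 + 2rho.

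**Step 2, standardised effects** (positive = favourable).
- All seven improve: 7d/√(7 + 42rho) aligned; 3d/√(7 + 2rho) unreversed.
- Function only: 2d/√(7 + 42rho) aligned; −2d/√(7 + 2rho) unreversed.
- Symptoms only: 5d/√(7 + 42rho) aligned; 5d/√(7 + 2rho) unreversed.

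At rho = 0.5 with all seven improving: 1.4/√28 = 0.265 against 0.6/√8 = 0.212, a ratio of 0.80.

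| rho | All seven: aligned | unreversed | ratio | Function only: aligned | unreversed | Symptoms only: aligned | unreversed |
|---|---|---|---|---|---|---|---|
| 0.3 | 0.316 | 0.218 | 69% | 0.090 | −0.145 | 0.226 | 0.363 |
| 0.5 | 0.265 | 0.212 | 80% | 0.076 | −0.141 | 0.189 | 0.354 |
| 0.7 | 0.232 | 0.207 | 89% | 0.066 | −0.138 | 0.166 | 0.345 |

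The ratio does not depend on d. On the raw scale the unreversed sum keeps 3/7 = 43% of the aligned shift. If one symptom domain and one function domain improve equally and nothing else moves, the net shift is 0.2 − 0.2 = 0. A benefit confined to symptoms shows more strongly in the unreversed sum, so the distortion can go either way.

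**Step 3, power** with all seven domains improving by 0.2 SD and rho = 0.5.

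| Completers per arm | Aligned | Unreversed |
|---|---|---|
| 447 | 0.977 | 0.887 |
| 678 | 0.998 | 0.974 |
| 845 | about 1.00 | 0.992 |

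**Step 4, weights.** 43 = 7×6 + 1 and 37 = 7×5 + 2. A sum over all items therefore either weights the domains unequally or includes items outside the seven. The definition does not say which.

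**Step 5, age forms.** Acute pain and depression enrol from age 8 (Section 5.1), and randomisation in both is stratified pediatric/adult (Section 4.1). Section 10.4 links the two depression T-scores before combining them. For overall well-being, Section 10.5 gives neither a link nor an age stratum. The synopsis describes an ANOVA adjusted for baseline differences, which does not name age form either.

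**The case against.** The strongest objection is that the documents never give item coding for the 43- or 37-item survey. Opposite directions are inferred from domain names, and the absence of reversal is inferred from silence. The one ability scale described, for the separate mobility instrument in Section 7.3, lists answers from no difficulty to unable, so same-direction coding is not excluded. Section 10.2 announces a detailed SAP for each trial in a separate document, which may hold the scoring rule. All of this stands, and the offset is therefore stated as conditional. It does not rescue the definition: if every item is coded higher = worse, a high well-being score means poor well-being, and Section 11.2 does not say that either.

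The consequences are also limited. The sub-domains are tested separately with their own T-scores, Section 10.6 plans a utility analysis from the adult form, and no primary analysis or sample size depends on this score. That limits the harm but leaves the summary endpoint undefined.

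On age, T-scores share a nominal centre and spread, and stratified randomisation balances age between arms. Pooling should therefore not systematically bias the arm comparison. The cost is in precision and interpretation, and Section 10.4 shows that the plan does not treat T-scores from the two forms as interchangeable.

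A reader might infer two stronger claims, and neither is supported. One is that functional and symptom benefits generally cancel. With five domains against two the offset is partial when all improve, and exact cancellation needs a special pattern. The other is that this is the only endpoint common to the trials, or the only one analysed in all randomised participants. Section 3.2 also lists the sub-domains and concordance for all trials, and Section 10.5 applies the same intent-to-treat comparison to the sub-domains.

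**Conclusion.** The point holds as an incompletely defined endpoint with a conditional loss. It is certain that Section 11.2 gives no reversal rule, favourable direction or conversion source for a score spanning problem and ability domains. It is also certain that Section 10.5 compares scores from two age forms without a link or the age stratum.

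The offset applies only if higher means more of the named domain and responses are summed as written. Under equal weights and a common correlation of 0.3 to 0.7, 69% to 89% of the aligned standardised effect remains when all seven domains improve equally. For a 0.2 SD benefit in function alone, the total moves about 0.14 SD the wrong way. If items are already aligned there is no offset, and the remaining defect is that the plan does not say so. The matter concerns a secondary endpoint and leaves the primary conclusions untouched.

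**What to change.** In Section 11.2, define overall well-being as the mean of the seven domain T-scores already planned for comparison in Section 10.5. Reverse physical function and social role (100 minus T) where higher means better. State that the domains carry equal weight and which direction is favourable.

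Score within each age form. In Section 10.5 and the synopsis, compare arms stratified by the pediatric/adult randomisation stratum in the acute pain and depression trials. Chronic pain enrols adults only and needs no age stratum.

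The cost is a revised definition and a few lines of code, with no new data. The small downside is that equal domain weighting becomes an explicit choice that the plan must state.

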## 5. STUDY POPULATION

### 5.1 Inclusion Criteria

#### Acute Pain

- Age  $\geq$  8 years
- English speaking or Spanish speaking
- Elective/planned surgery types with planned or anticipated to be treated with tramadol, hydrocodone, or codeine pain management at an enrolling site, which may include orthopedic surgeries(e.g. arthroplasty, spine, etc.), open abdominal surgery, or cardiothoracic surgery and others

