## 7.2 Baseline Participant Assessments

All study participants will complete baseline surveys for demographics and participant reported outcomes (PROs) (see Table 8 for details). These data will be collected by the study coordinator in person or alternatively by using telephone, email, or text.

Baseline data will be collected for the Chronic Pain and Depression trials following consent, for the Acute pain trial, survey data will be collected before surgery. The type of surgery information will be collected after the completed procedure.

*Participant demographics* – including but not limited to age, sex, gender, race, Hispanic/Latino ethnicity (Yes or no), and smoking status will be administered at baseline as a survey.

*Past medical history* – A snapshot of the participant's medical history. See MOP for details.

*Baseline medications* - Participant medications will be collected through the EHR and/or participant self-report. See MOP for details.

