## **10. STATISTICAL ANALYSIS PLAN AND SAMPLE SIZE**

### **10.1 Sample Size Determination**

All trials power analyses are based on a modified intent to treat analysis, comparing the subset of intervention participants with have an actionable phenotype to the subset of control participants with an actionable phenotype. Effect sizes used to estimate power are based on prior studies of pain and depression pharmacogenetic testing and described below for each trial and shown in Table 8. Several steps were taken to generate a conservative sample size estimate. First, the power requirement was set to 90%. Second, sample sizes are adjusted for a 10% drop-out (for which UF has data from several studies that this is a good estimate). Third, slightly smaller effect sizes than what was observed in prior studies was used. Finally, sample size calculations are based on an alpha of 0.049, to allow one interim analysis with an alpha of 0.001 in each study.

Due to the study design and the delay in the control arm to obtaining the genotyping results required determine the actionable phenotype subgroup assignment, it is not feasible to directly monitor the number of randomized participants in the actionable subgroup for the enrollment stopping rule. Alternatively, the observed trial specific actionable phenotype percentages and the corresponding trial specific total enrollment targets will be used to identify when enrollment can conclude for a fully powered mITT study.

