#### Acute Pain

In the University of Florida's pilot acute pain study, the difference between study arms in SIA score was -38.55 with a SD of 93.5, for a standardized effect size of 0.412. Assuming a reduced standardized effect size of 0.375, 304 participants with an actionable phenotype per group, 152 from the intervention arm and 152 from control arm, are required to achieve 90% power for a two-sided two-sample t-test. Preliminary data from the University of Florida's acute pain study indicates the proportion of participants with an actionable phenotype, genotypic or pheno-converted CYP2D6 IM or PM, will be approximately 18%. After adjusting for the subset anticipated to have an actionable phenotype, 845 participants completing all assessments, per group, are required to achieve 90% power in the sub-group analysis (1678 total). Assuming 10% drop out or lost to follow-up and 7% of participants not going on to surgery, a total of 2020 randomized participants is required to sufficiently power this study. Factoring in variability in the proportion that are IMs or PMs (15% to 24%), 1516 to 2424 randomized subjects would be need to achieve 90% power in the mITT analysis.

Chronic Pain: In the University of Florida's prior chronic pain study, the difference between study arms in composite pain score was 0.6 with a SD of 1.4, for a standardized effect size of 0.43. The same effect size was observed when assessing 3-month changes in pain scores. Assuming a standardized effect size of 0.40, 268 participants within the specified subgroup, 134 from the intervention arm and 134 from control arm, are required to achieve 90% power for a two-sided two-sample t-test. Preliminary data indicate the proportion of participants with an actionable phenotype will be 30-35%; 10-15% of participants with an actionable genotype-based phenotype (CYP2D6 IM or PM) and an additional 20% with a pheno-converted PM/IM based on drug-drug-gene interactions. After adjusting for the subset anticipated to have an actionable phenotype, 447 participants completing all assessments, per group, are required to achieve 90% power in the sub-group analysis (894 total). Assuming 10% drop out or lost to follow-up, a total of 994 randomized participants is required to sufficiently power this study. Factoring in variability of the proportion of randomized population that are IMs or PMs (24-33%), 906 to 1244 randomized subjects would be need to achieve 90% power in the mITT analysis.

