Pain control: The difference in pain intensity score at follow-up time t and the baseline pain intensity score.

Pain intensity score: The mean of average pain in the last 7 days, current pain, and worst pain in the last 7 days. Average pain, current pain, and worst pain will be collected using the 3-question PROMIS pain intensity scale.

Pain reduction score: The ratio of the pain intensity score (derived from the PROMIS pain intensity survey) at follow-up time t to the baseline pain intensity score.

Silverman integrative analgesic assessment (SIA) score: This is an integrated measure of pain and opioid usage, calculated as follows: pain and opioid usage are ranked, the ranks are converted to percentiles and linearly transformed such that the scores are centered at 0 and range -100 to 100. The pain scores and opioid usage transformed percentiles are summed to generate the SIA score that ranges -200 to 200. Negative values indicate low pain with minimal opioid usage, while positive values indicate higher pain with higher opioid usage. See Appendix A for additional details and supporting rationale.

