## 14. APPENDICES

### 14.1 APPENDIX A. SIA SCORE BACKGROUND AND RATIONALE

For the primary endpoint, we propose to use a composite score that captures both opioid consumption (MED) and pain intensity. This is based on preliminary data from a University of Florida (UF) pilot study in which CYP2D6 genotype-guided opioid prescribing after arthroplasty surgery was compared to a usual care approach (ClinicalTrials.gov Identifier: NCT03534063). While not powered to detect differences in clinical endpoints, preliminary results from 174 patients showed similar pain intensity at 2-week post-surgery between genotype-guided and usual care groups, but significantly lower MMEs in the genotype-guided group. The combination of lower opioid consumption with similar pain intensity indicates better pain control in the genotype-guided arm. However, assessing opioid consumption and pain intensity as two separate variables fails to characterize the inter-individual differences in opioid use as pain intensity changes over time, which is why we believe a composite endpoint that integrates the two is justifiable.

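### The acute pain primary score is ranked with no stratum named and tested without adjustment for surgery type or age group, so its 90% power holds only if operations and ages differ little or the planning margin covers the difference

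*Combined protocol and SAP*

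**What the plan says.** Section 11.2 (Data Element Definitions) builds the SIA score from two components: "pain and opioid usage are ranked, the ranks are converted to percentiles and linearly transformed such that the scores are centered at 0". The two are then added. Neither 11.2 nor Appendix A says who is ranked (all randomised, or only those with an actionable phenotype) or whether ranks are formed within any stratum. Opioid usage in 11.2 is average daily morphine equivalents in mg.

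The acute pain trial takes participants from age 8. Section 5.1 admits many operations: "which may include orthopedic surgeries(e.g. arthroplasty, spine, etc.), open abdominal surgery, or cardiothoracic surgery and others". Section 4.1 stratifies the acute pain randomisation by pediatric/adult. Section 7.2 records the operation: "The type of surgery information will be collected after the completed procedure".

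Section 10.4 compares 10-day SIA scores between arms with a two-sample t-test or Mann-Whitney test at 0.049, with no covariates. Surgery type appears only in section 10.6, as a possible covariate in exploratory repeated-measures models.

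For sample size, section 10.1 reports that in the University of Florida acute pain pilot "the difference between study arms in SIA score was -38.55 with a SD of 93.5, for a standardized effect size of 0.412", and plans on 0.375. Appendix A describes a University of Florida pilot in which "genotype-guided opioid prescribing after arthroplasty surgery was compared to a usual care approach".

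**The concern.** A rank-based score has a fixed spread: each component runs from -100 to 100 whatever the population. In a single operation, that spread reflects differences between patients having the same procedure. In a list that mixes arthroplasty, spine, abdominal and cardiothoracic surgery, and children with adults, part of the spread goes to differences between operations and ages. A given benefit within an operation then moves a participant past fewer others, and the arm difference becomes smaller relative to the SD.

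A planning effect measured in one type of surgery is therefore not on the same scale as the score this trial would compute from a pooled list. The power of the acute pain primary test is at stake. Two variables that could recover the loss, the pediatric/adult stratum and surgery type, are already recorded, and the primary analysis uses neither.

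**Working it through.** **Inputs from section 10.1.** Two-sided alpha 0.049 ("sample size calculations are based on an alpha of 0.049, to allow one interim analysis with an alpha of 0.001 in each study"), 90% power, 152 per arm, planning effect 0.375, pilot effect 38.55/93.5 = 0.412.

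**The plan's own figure.** Power = Φ(d√(n/2) − z), with z = 1.969 for alpha 0.049 and √(152/2) = 8.718. At d = 0.375: Φ(3.269 − 1.969) = 90.3%; the exact t calculation gives 90.1%. Randomised total: 304/0.18/0.90/0.93 = 2,018, against 2,020 stated. The arithmetic is right.

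**Correlation implied by the pilot SD.** A component uniform on −100 to 100 has variance 200²/12 = 3,333. The sum of two has variance 2 × 3,333 × (1 + r). Setting this to 93.5² = 8,742 gives r = 0.31.

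**Effect of pooling.** Let b be the share of each component's variance that lies between surgery/age groups. The documents do not give b; 10, 20 and 30% are assumed. On a standardised scale the sum of the components has
- within-group variance 2(1 − b)(1 + r);
- between-group variance 4b if group effects on pain and opioid use are aligned (the more painful operation is also the higher-opioid one), 2b if they are unrelated, and 0 if they are opposed.

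If s is the between-group share of the sum, the pooled effect is d√(1 − s). Example, aligned with b = 0.20: s = 0.80/(0.80 + 2 × 0.80 × 1.31) = 0.276; d = 0.375 × √0.724 = 0.319; power = Φ(0.319 × 8.718 − 1.969) = 79%.

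Power at 152 per arm, from this formula:

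| Within-operation effect | Group pattern | b = 10% | b = 20% | b = 30% |
|---|---|---|---|---|
| 0.375 | aligned | 85% | 79% | 72% |
| 0.375 | unrelated | 88% | 85% | 81% |
| 0.375 | opposed | 90% | 90% | 90% |
| 0.412 | aligned | 91% | 86% | 80% |
| 0.412 | unrelated | 93% | 91% | 88% |

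**Check by simulation of ranked scores** (152 per arm, five equal groups, homogeneous effect about 0.375). Aligned: 84–86, 79–80 and 71%. Unrelated: about 88, 85–86 and 81–83%. Opposed: about 90% throughout. With 0.412: 92, 86 and 79% aligned; 94, 91 and 88% unrelated. These agree with the table.

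**If the assumed share is of the SIA score itself** (s rather than b), power at 0.375 is 87, 83 and 78% for s = 10, 20 and 30%. Restoring 90% by numbers alone would take 167, 188 and 215 per arm, or about 2,220, 2,500 and 2,850 randomised at 18% actionable.

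**What the planning margin covers.** Power stays at 90% with a true 0.412 until 0.412√(1 − s) = 0.375, so s = 1 − (0.375/0.412)² = 0.17. Solving the variance expressions above for b, this is b of about 12% if aligned and about 21% if unrelated.

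**What adjustment does.** Ranking within groups, or adjusting the pooled score for group, held simulated power at about 90% in the settings above. With no group differences it cost about one percentage point or less (in one run, 89.1% pooled, 88.4% adjusted, 88.0% ranked within groups). Null rejection was 5.2–5.5% for all three methods at nominal 4.9%.

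**The case against.** The strongest objection is that the size of the loss rests on quantities the documents do not give. There is no case mix, no number of children and no between-operation variance. The larger losses need pain and opioid use to vary together across operations. That is not assured: opioid use in mg without regard to body size would shift a child's opioid rank but not the pain rank. Other sections suggest a narrower mix than 5.1 permits. Section 6.1 approaches providers who mainly use three named opioids and gives priority to procedures with persistent pain at 10 days, and section 9.1 draws on knee and hip arthroplasty figures when estimating claims coverage. The plan also cut the effect from 0.412 to 0.375. All of this stands, and it is why the loss is stated as conditional.

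A reader might infer that the plan fails to deliver its 90% power. The documents do not support that: the calculation is correct for 0.375, and a moderate amount of heterogeneity is covered if 0.412 is the true within-operation effect. But the plan presents the cut as general caution and never mentions case mix, so pooling would spend a margin meant for other uncertainties.

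A reader might also take pooled ranking, and the arthroplasty origin of 0.412, as stated facts. The first is the natural reading of a silent text. The second is a strong inference from section 10.1 and Appendix A. Section 10.2 defers detail to a separate SAP, which may settle the ranking set, but 10.4 already fixes an unadjusted test. The exploratory covariate models in 10.6 leave that primary test unchanged.

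**Conclusion.** The point holds as a conditional loss of efficiency. The sample size of 152 per arm is right for an effect of 0.375. Whether the analysed score will show that effect depends on how much pain and opioid use differ between operations and ages, and on whether those differences run together. Under assumed shares of 10–30% per component, the pooled, unadjusted comparison ranges from no loss (opposed patterns) to about 71% power (aligned, 30%, true effect 0.375). If 0.412 is true, power is at or above 90% in the milder cases and falls to about 79% in the worst one shown. The unadjusted test remains valid, so a reader should not infer bias or a false-positive problem. The change is worth making because it recovers the loss wherever it exists and costs almost nothing where it does not.

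**What to change.** 1. In section 10.4, Acute Pain, make the primary comparison a linear model of the SIA score on arm, with pediatric/adult and a prespecified surgery-type grouping as factors. An essentially equivalent option is to form the ranks in 11.2 within those strata and keep the two-sample test.
2. In 11.2, state who is ranked and, if ranks are stratified, by what. Merge small groups (for example, under 20 participants) by a fixed rule.
3. Use the planned procedure for the grouping, or the recorded one with a statement that the arm cannot affect it.
4. Keep the pooled, unadjusted test as a sensitivity analysis.
5. In 10.1, say which pilot patients gave 0.412 and show power over a range of between-group variance.

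The cost is about a paragraph of SAP text and a list of surgery groups, both fixed before unblinding. No extra data or participants are needed. The small downside is coarse ranks in small groups if the within-stratum option is chosen, which the merging rule limits.
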